Increasing Steps/day with Wearable Step Counters: Steps/day is an increasingly utilized metric for objectively capturing and representing total daily walking.^{24,25} Researchers recently reported 5-year changes in body mass index (BMI), waist-to-hip-ratio, and insulin sensitivity related to 1,000 step incremental changes in step-defined physical activity.²⁶ Meta-analyses indicate that step-counting interventions can expect to realize incremental increases in walking behavior on the order of 2,000-2,500 steps/day. The Co-Investigator of this R21 is a world leader in such interventions.^{25,27,28} She developed a self-selected goal approach that elicited up to an extra 4,000 steps/day in individuals with Type 2 diabetes,² and was subsequently adapted and delivered as a workplace intervention that elicited a 3,500 steps/day change.¹ As reported in a recent meta-analysis,²⁹ at least four other controlled workplace studies have incorporated wearable step-counters into multi-component interventions. The inclusion of a pedal desk is novel. No one has previously estimated the relative contributions of independent intervention components to changes in abdominal obesity.

A Combined Approach: Pedaling actions are largely ignored by waist-worn step counters.³⁰ Therefore, layering a step-counting intervention on top of a pedal desk intervention permits a clear evaluation of their separate and combined dose-response effects. Daily electronic tracking of pedal desk use (duration, rpm, estimated distance and energy expenditure) and steps/day via automatic internet-based software enables continuous tracking of both behaviors for tailored feedback, behavioral shaping, and evaluation purposes. **WorkACTIVE-P** will clearly inform the feasibility of combining these distinct yet compatible components of a workplace multi-component energy expenditure intervention.

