Expected Outputs and Outcomes: **WorkACTIVE-P** will provide clear feasibility and preliminary effectiveness evidence for a combination of practical technology-supported products and programs for Service Industry employers and workers interested in addressing health risk exposures (and related health care costs) associated with occupational sedentary behavior.

Innovation:

The innovation of **WorkACTIVE-P** is based on the following tenets:

- 1) Occupational requirements for extended sedentary behaviors in contemporary workplaces have disrupted the energy balance equation and present a real risk for weight gain, abdominal obesity, and corollary conditions.
- 2) The health care costs of low energy expenditure occupations are not trivial and are borne by the individual workers, employers, and society.
- 3) Abdominal obesity is a driving force of the metabolic syndrome but appears amenable to aerobic exercise and even light intensity physical activity interventions.
- 4) Traditional workplace wellness programs focused on exercise and fitness have reported modest adherence and limit the opportunity to re-balance the occupational energy expenditure deficit to time outside of work.
- 5) Workplace deliveries of interventions that use wearable step counters to increase lifestyle physical activity have demonstrated some short term success.
- 6) Further elevating energy expenditure by replacing sedentary working behaviors with tolerable low intensity non-exercise physical activity via scalable active workstations (e.g., pedal desks) is a promising strategy.
- 7) Uniquely, we have fashioned an affordable, convenient, integrated and user-friendly pedal desk: a semi-recumbent (upright) portable pedaling station with an attached, maneuverable, adaptable desktop capable of supporting a large computer monitor. This is an improvement over “under desk” designs.
- 8) No study has documented the separate and potentially synergistic effects of a behaviorally supported, multi-component workplace energy expenditure intervention that layers step counting on top of pedal desk use.
- 9) Moving the study of workstation alternatives out of the laboratory and into real workplaces is necessary to assess scalability and track real patterns of use, ultimately informing their true potential to elevate workplace energy expenditure.

a. Specific Aims:

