The objective of WorkACTIVE-P is to conduct a preliminary outcome evaluation of an innovative multi-component intervention focused on raising energy expenditure and re-balancing the disrupted energy balance equation of sedentary workplaces with an ultimate target of reducing workers' abdominal obesity. The energy expenditure intervention includes replacing workplace sedentary time with access to a dedicated pedal desk and increasing steps/day with wearable monitors. Both components are incorporated into an electronically-delivered behavior monitoring and support infrastructure, thus enabling continuous management. This pilot study is a necessary step towards our long term goal to conduct an RO1 investigation to exactly quantify the separate and combined dose-response effects of this multi-component intervention on promoting healthy weight management, and in particular, abdominal obesity in the sedentary workplace.

Recent evidence suggests that contemporary sedentary behaviors may contribute to the obesity epidemic and trigger the development of cardiovascular disease and Type 2 diabetes.³ Because occupational sitting is the single largest contributor (52%) to total weekday sitting time,⁴ employment in a sedentary occupation may represent a risk factor for weight gain, especially among those who are physically inactive during leisure-time.^{3,5} Workers employed in such low energy expenditure occupations (e.g., typists) are 63% more likely to be abdominally obese (>102 cm in men and >88 cm in women) compared to workers in high energy expenditure occupations (e.g., construction trades).⁶

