Primary Aim: The primary outcome is the change in abdominal obesity operationalized as MRI-determined visceral adipose tissue (VAT). Over the course of a 2-year period and working collaboratively with a real workplace, **WorkACTIVE-P** will randomly assign 41 low active (< 7,500 steps/day), overweight/obese sedentary full-time workers (reporting "mostly sitting" during the work day), 18-64 years of age, with abdominal obesity defined by waist circumference and at least one additional component of the metabolic syndrome (dyslipidemia, elevated blood pressure, and/or impaired fasting glucose¹²), to a 3-month-long controlled trial. The trial will include baseline and 3 month assessments and two intervention arms: 1) a combined electronic behavior support program of "walk more and pedal desk" (WMPD, n=20), which, in addition to provision of a dedicated pedal desk in individual worker's office space, participants are supported to increase daily walking by at least 3000 steps/day; and 2) a no-intervention control condition (CON, n=20). This design allows us to test the hypothesis that: this innovative multi-component workplace energy expenditure intervention will elicit measureable improvements in abdominal obesity superior to the control condition. Relative contributions of the two intervention components (walk more and pedal desk) will be determined by regression analyses predicting VAT changes.

Additional Aims: Secondary outcomes include changes in body weight, total adipose tissue, subcutaneous adipose tissue, blood pressure, blood lipids, fasting glucose and insulin, [HbA1c], free-living accelerometer-determined walking (steps/day and cadence), time spent in sedentary behavior, exercise (time spent at moderate-to-vigorous physical activity), and dietary intake. We will electronically track daily steps data for WMPD participants and also duration of use and cadence (revolutions per minute, or RPM) of dedicated pedal desks. After completion of this pilot study, a subsequent R01 will be proposed to perform a full-scale RCT to quantify the separate and combined effects of the intervention components on change in the study endpoints.

III. Overview of Research Design

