- **Dietary Intake:** Food intake data will be captured with the Remote Food Photography Method (RFPM) using participants' personal (or one of our loaned) smartphones. The RFPM and SmartIntake© app (previously developed and validated by study Principal Investigator, [name] and colleagues^{38,39}) will be used to collect energy and nutrient intake data at baseline and month 3. Participants will use the procedure to photograph and track their dietary intake for 7 consecutive days, with the first 1-2 days being a run-in period to acclimate participants to the procedure, resulting in approximately 4-5 complete days of data per participant. Three days of recorded food intake has been shown in several studies to provide an accurate estimate of average food intake;⁴⁰⁻⁴² hence, we are collecting ample data to obtain a representative sample of habitual food intake.
- **Height and weight:** Height and weight will be measured to the nearest 0.1 kg using a standard stadiometer and balance beam scale, according to Pennington Biomedical's SOP.
- **MRI-determined visceral adipose tissue (VAT; indicator of abdominal obesity):** Magnetic resonance imaging (MRI) will be performed using a 3.0 T scanner (General Electric, Discovery 750w System, Milwaukee, WI). Subjects will in a supine position on the scanner table with the arms above the head. Subcutaneous fat, visceral fat, and muscle compartments will be traced on each slice by a trained analyst using Analyze™ software (AnalyzeDirect, Overland Park, KS) and a standardized tracing protocol.
- **Step-counter:** Participants will be instructed to wear the NL-1000 pedometer or a similar model at their waist for seven consecutive days. Fitbit Zip© devices may be worn in place of the pedometer during the Run-In period as needed.
- **Waist circumference:** Waist circumference will be taken according to Pennington Biomedical's SOP and measured to the nearest 0.1 cm.

VII. Interventions

Participants will be randomized into 1 of 2 intervention arms: Usual Working Condition Control group (UWC) or a combined intervention of Walk More and Pedal Desk (WMPD).

- a. **Usual Working Condition Group (UWC):** The no-intervention control condition will be asked to maintain their usual work and lifestyle throughout the study. Participants may be contacted by Pennington Biomedical staff during the intervention.

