- b. **Combined Intervention (Walk More and Pedal desk; WMPD):** Participants in the WMPD condition will engage in both step-counting (Walk More, WM) and pedal desk (PD) intervention components. The content of both intervention components will be covered during scheduled phone contacts (or in-person meetings, as needed). The step-counting component of the WMPD intervention will be modeled off the success of The First Step Program (FSP), originally developed by [name]. Briefly, the FSP is a facilitated behavior modification program built on the framework of Social Cognitive Theory (SCT),^{43,44} emphasizing the components of self-efficacy and social support.⁴⁵ Participants will be given internet-enabled step-counting devices (Fitbits). Participants will be taught how to manage their own stepping behavior by regularly checking the on-board visual display and also by monitoring the accompanying internet reporting software to track their own average steps/day each week. [name] has successfully piloted this technology to also provide interventionists with an opportunity to view participants' data as they accrue. We have implemented this same interventionist-supported behavior change and monitoring approach on numerous occasions.^{2,46-49} Using these same techniques to collect pilot data for WorkACTIVE-P, we successfully motivated 98 participants averaging 4973 steps/day during at baseline up to an average of 9692 steps/day (max 13971) during a three month pedometer-based intervention, an average increase of almost 5,000 steps/day. We are thus confident that participants assigned to WMPD condition in WorkACTIVE-P will be easily able to increase their daily ambulatory activity at least 3,000 steps,^{50,51} and much likely more as confirmed by our pilot data.

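### The Primary Aim says regression will determine the separate contributions of walking and pedalling, but the two-arm design supports only an exploratory, non-randomised association

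*Combined protocol and SAP*

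**What the plan says.** Section II.b (Primary Aims and Hypotheses), in the Primary Aim paragraph: "Relative contributions of the two intervention components (walk more and pedal desk) will be determined by regression analyses predicting VAT changes". Section II, under A Combined Approach, says that adding step counting to the pedal desk "permits a clear evaluation of their separate and combined dose-response effects".

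On assignment, section VII.b says: "Participants in the WMPD condition will engage in both step-counting (Walk More, WM) and pedal desk (PD) intervention components". Section VII.a says of the other arm: "The no-intervention control condition will be asked to maintain their usual work and lifestyle throughout the study". There is no walking-only or pedalling-only arm.

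On dose, section VII.b says of walking: "Participants will be taught how to manage their own stepping behavior". Sections II.b and VII.c set a shared walking target of at least 3,000 extra steps/day. Pedal-time goals are personal and depend partly on work schedule, and support is stepped up when adherence is poor (both VII). Pedalling pace is self-selected (VIII.a).

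Other text is more cautious. Expected Outputs and Outcomes (section II) says the study "will provide clear feasibility and preliminary effectiveness evidence for a combination of practical technology-supported products and programs". Section II.a calls the study a pilot and gives as the aim of a later investigation "to exactly quantify the separate and combined dose-response effects of this multi-component intervention". The Additional Aims paragraph of II.b says "a subsequent R01 will be proposed to perform a full-scale RCT to quantify the separate and combined effects".

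Section IX.a powers only WMPD versus CON. Section IX.d tests that contrast and summarises adherence measures by week, but gives no dose variables, analysis set, adjustment or status for a component regression.

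**The concern.** A randomised trial can attribute an effect to a component only if the component varies by assignment. Here both are switched on or off together. The split is left to a regression on the doses participants reached, and those can also reflect motivation, type of job and the support received.

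The Primary Aim says this regression will determine relative contributions. A report that followed the text could present an observational division of VAT change between walking and pedalling as a determined result under the Primary Aim, and the planned R01 could be designed around it. The randomised evidence would support a conclusion only about the combination.

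**Working it through.** **1. What randomisation identifies.** Code assignment as (walk, pedal). WMPD is (1, 1) and control is (0, 0). With main effects W and P and interaction I, the expected arm difference is W + P + I. That is one randomised contrast for three unknowns. No sample size in this two-arm design separates them.

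**2. Where the split would have to come from.** Only from differences between people in achieved dose. Pedal time follows personal goals. Walking has a common floor, but the amount above or below it is left to the participant. Support rises when adherence falls, so it also moves with dose. None of this variation is assigned. Pooling the control arm adds almost nothing for pedalling, because controls have no pedal desk and so no pedal dose.

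**3. The plan's own sample size, reproduced.** Inputs from IX.a: difference 1.15 kg, SD 1.20 kg, 80% power, 10% attrition; two-sided alpha 0.05 (IX.a, IX.d).
- n per arm = 2 × [1.20 × (1.960 + 0.842) / 1.15]² = 17.09, rounded up to 18.
- Power at 18 per arm is 82.0% by normal approximation and 79.8% by the t test.
- 18 / 0.90 = 20 per arm.

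The stated 18 and 20 are reproduced. They cover the package contrast only.

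**4. Precision of a relative contribution.** This is a comparison of two slopes. For two standardised doses with correlation ρ and residual SD s, the half-width of the 95% CI for their difference is t × s × √{2 / [(n − 1)(1 − ρ)]}. The documents give neither ρ nor s for this model. I assume s = 1.20 kg (the SD in IX.a) and ρ from 0 to 0.7. With n = 18 there are 15 residual df and t = 2.131.

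| ρ | SE of difference (kg) | 95% half-width (kg) |
|---|---|---|
| 0 | 0.412 | 0.88 |
| 0.5 | 0.582 | 1.24 |
| 0.7 | 0.752 | 1.60 |

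With n = 20 (17 df, t = 2.110) the half-widths are 0.82, 1.16 and 1.50 kg. The units are kg per SD of dose, so the planned 1.15 kg is a yardstick for scale and not the same quantity. If adjusting for baseline VAT lowers s, the half-widths shrink in proportion.

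**5. Precision of one slope (secondary).** This treats doses as random and uses the model in the fix (steps, pedal time, baseline VAT). The partial correlation of 0.3 is an assumption.
- n = 18: 80% power needs a partial correlation of 0.64; power at 0.3 is 21%.
- n = 20: 0.61 and 23%.
- Fisher interval for an observed 0.3 with n = 18: atanh(0.3) = 0.310 and SE = 1/√(18 − 2 − 3) = 0.277, giving −0.23 to 0.69. With n = 20 it is −0.19 to 0.67.

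A fixed-predictor calculation without baseline VAT gives slightly more favourable figures at n = 18 (0.58 needed; 24% at 0.3). The message is the same.

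**The case against.** The strongest reply is that, read whole, the protocol does not treat this regression as confirmatory. II.b states one hypothesis, package against control. The regression has no hypothesis, power claim or test of its own. II.a calls the study a pilot, and both II.a and the paragraph after the disputed sentence reserve quantification of separate effects for a later trial. On that view the dispute is about one verb.

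Much of this stands, and it is why the point is about wording and specification and does not undermine the trial. It does not dispose of the point. The sentence sits inside the Primary Aim, the background promises a clear evaluation of separate effects, and no passage labels this regression exploratory. The word for preliminary in Expected Outputs qualifies effectiveness evidence for the combination and says nothing about the split.

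A reader might go further in four ways that the documents do not support:
- **That both doses are freely self-selected.** Walking has a shared target of at least 3,000 extra steps/day. The accurate statement is that achieved dose is not randomised.
- **That the component estimates will be confounded.** The documents do not show this; the design simply does not rule it out.
- **That small numbers are the root fault.** Precision is a second limit. A larger two-arm trial would still not randomise the split.
- **That the primary comparison is compromised.** It does not depend on this regression.

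**Conclusion.** The claim in II.b is stronger than the design allows and should be changed. Randomisation supports a conclusion about the combined package only; the regression can describe how achieved walking and pedalling relate to VAT change among people given both. This follows from the assignment structure and needs no numerical assumption.

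The precision figures are illustrative. They rest on 18 to 20 WMPD completers and on an assumed residual SD, dose correlation and partial correlation. Over those ranges, the uncertainty in a walking-versus-pedalling comparison is of the same order as the effect planned for the whole intervention.

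This is worth correcting before analysis. It does not affect the validity of the WMPD versus CON result.

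**What to change.** 1. In II.b, replace the sentence with:

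> Associations of achieved step change and pedal-desk time with VAT change will be explored within the WMPD arm, adjusted for baseline VAT, and reported with 95% CIs as exploratory and non-randomised, without causal attribution to either component; the randomised comparison estimates only the effect of the combined package.

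2. In section II, A Combined Approach, bring the statement about evaluating separate and combined dose-response effects into line with this.

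3. Add the same analysis to IX.d, with its analysis set (WMPD arm), dose variables and covariate. Take step change from the accelerometer data collected at baseline and month 3, so that both ends are measured with the same device; the intervention Fitbit has no matching baseline in the plan. Pedal time comes from the desk-tracking software.

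Adjusting for baseline VAT does not remove confounding by motivation, job type or support, so the exploratory label is still needed.

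The cost is three short text changes and a more modest claim. Accelerometry samples one week at each end, so step change will not describe the whole intervention period. No new data are needed and the primary analysis is unchanged.

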Interested participants who are deemed eligible on the online screening survey, received supervisor approval to participate, and complete the phone screen will attend a 1-hr orientation visit conveniently located at their worksite where they will receive detailed information on the purposes, goals, procedures, participant flow, timeline, and randomization. Interested participants will be offered an informed consent form to continue. Participants will sign two copies of the informed consent and will be able to keep one copy. All questions and concerns will be clarified prior to participants signing the form or conducting any procedures. Participants will be scheduled for their run-in visit and provided a step counter (pedometer or Fitbit Zip) which requires 1 week (7 days) of self-monitored step counter-determined physical activity.

Run-In:

A Run-In visit will occur approximately one week after Orientation and will be held at their workplace. At the Run-In visit, initial inclusion/exclusion criteria will be assessed (e.g., BMI, waist circumference, blood pressure). Participants will return the step counter to determine their ability to self-monitor behavior and further confirm baseline eligibility (< 7,500 steps/day) from the step-counters retrieved at their workplace. Participants will complete questionnaires related to physical activity, medical history, and demographic information. Those who continue to remain eligible will be scheduled for an in-clinic screening visit (SV1) held at the Pennington Biomedical Research Center. Participants may be asked to repeat measures based on the PI's discretion.

Screening Visit 1:

At Screening Visit 1, which will occur as early as two working days after the Run-In visit, participants will have a blood draw to measure fasting levels of glucose, insulin, HOMA-IR, HbA1c and blood lipids. Anthropometrics will be taken during SV1 including height, weight, BMI, blood pressure, heart rate, and waist circumference. Food intake data will be captured with the Remote Food Photography Method (RFPM) using participants' personal (or one of our loaned) smartphones to collect energy and nutrient intake data. Participants will be distributed an Actigraph Accelerometer (GT3X⁺) and will be instructed to wear the device for one week (7 days). After lab results are available, study staff will confirm if the participant is eligible to continue based on the inclusion criteria.

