If more than 16 days lapse between SV and Baseline scheduled date, participants may be asked to repeat measures to re-assess eligibility.

Baseline Visit:

Eligible participants after SV1 will return to Pennington Biomedical Research Center approximately one week but up to 16 days after SV1 for a Baseline Visit. Participants will return the accelerometer to further evaluate each participant's ability to comply with the wearing requirement of objectively monitored devices (i.e., at least 4 days with at least 10 hours of wear time recorded), allowing us to exclude participants with poor adherence to study requirements. Accelerometer data (physical activity and sedentary behavior) obtained during this screening process will serve as participants' baseline accelerometry data. An MRI will be completed to collect visceral fat, subcutaneous fat, and muscle compartments. Female participants will have a urine pregnancy test before the MRI. Randomization will occur at the conclusion of the Baseline Visit. Using a computerized pseudo-random number

generator, the study statistician will determine the randomization order in advance. The participants will be enrolled as directed by the next assignment letter contained in a randomized sequence of sealed and numbered envelopes. The project manager or interventionist (i.e., unblinded staff member) will reveal the randomization assignment to the participant. The participant will be provided with a behavioral expectations document informing them of the expectations of their randomized group. Study assessment staff will remain blinded to a participant's study arm allocation.

Month 3 Follow Up:

Randomized participants will return to Pennington Biomedical Research Center for a Follow-Up Visit approximately 3 months after intervention starts. Participants will return an accelerometer that was provided to them 1 week prior at their work place. Participants will complete questionnaires related to physical activity. All measures collected at the Screening and Baseline Visits will be repeated (blood work, body measurements, MRI, and RFPM). Female participants will have a urine pregnancy test prior to the MRI.

a. Description of Tests and Procedures:

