- **Accelerometry (Physical Activity):** Participants will be instructed to wear the GT3X+ accelerometer (ActiGraph, LLC, Pensacola, Florida, USA) at their waist for seven consecutive days, approximately 24 hrs/day. We have successfully used this 24-hour protocol in diverse populations including children, adults, and older adults and find it maximizes wear time. This accelerometer has been validated^{35,36} and is one of the most widely used accelerometers in research and has the capability of detecting minute-by-minute physical activity intensity and sedentary behavior using previously validated activity count cut points.^{36,37} Participants enrolled in the WMPD Intervention Group will be fitted with a FitBit® activity monitor to wear at their waist during the intervention. Participants will be asked to wear the FitBit® for all 12 weeks of the intervention, removing it only for activities involving water, such as baths or swimming, and while sleeping.
- **Blood Draws:** Participants will be asked to fast at least 12 hours prior to blood draw. In addition, participants will be asked to refrain from consuming alcohol or participating in an exercise training session at least 24 hours prior to blood withdrawal. Fasting levels of glucose, insulin, HOMA-IR, HbA1c, and blood lipids will be analyzed. Approximately 12 mL of blood will be collected at SV1 and Month 3 visits, which is a total of 24 mL during the course of the study.
- **Blood pressure:** Blood pressure will be measured at rest. Two measures will be taken with a heart rate in between. The average will be recorded per standard Pennington Biomedical's procedures.

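### The baseline accelerometer week follows the blood draw but the month-3 week ends at it, so only month 3 includes the pre-draw exercise request, and activity change may be slightly understated

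*Combined protocol and SAP*

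**What the plan says.** **Baseline (section VI, Screening Visit 1 and Baseline Visit).** Blood is drawn at Screening Visit 1 (SV1). The accelerometer is handed out at that visit, worn for seven days and returned at the Baseline Visit. The data "obtained during this screening process will serve as participants' baseline accelerometry data". Table 3 shows no blood draw at the Baseline Visit.

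**Month 3 (section VI, Month 3 Follow Up).** The order is reversed: "Participants will return an accelerometer that was provided to them 1 week prior at their work place". The same section says that the blood work is repeated at this visit. Section VI.a confirms that there are only two draws: "Approximately 12 mL of blood will be collected at SV1 and Month 3 visits".

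**Pre-draw request (section VI.a, Blood Draws).** Besides fasting, "participants will be asked to refrain from consuming alcohol or participating in an exercise training session at least 24 hours prior to blood withdrawal".

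**Outcomes (section II.b, Additional Aims).** Accelerometer-measured walking, sedentary time and MVPA are secondary outcomes, and the MVPA outcome is labelled exercise. Section IX.d gives no rule for accelerometer days that fall in the pre-draw period.

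**The concern.** A change score assumes that its two measurements were taken under the same conditions. Here one window carries an instruction about physical activity and the other does not, and the behaviour named in the instruction is close to one of the outcomes.

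The accelerometer is the only objective activity measure planned in both arms at month 3. The Fitbit and the pedal-desk log are for the Walk More Pedal Desk (WMPD) arm only, so they cannot supply the between-arm contrast. If month-3 activity is understated, the evidence that the intervention changed behaviour is weakened. A small observed difference would also be open to dispute over whether it was real or an effect of scheduling.

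**Working it through.** **1. The two windows side by side**

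| | Baseline | Month 3 |
|---|---|---|
| Device issued | SV1, the visit with the blood draw | Workplace, 1 week before the visit |
| Device returned | Baseline Visit, no draw | Follow-Up Visit, with draw |
| Position of the 24 h before the draw | Before the week starts | End of the week |
| Recorded days under the request | 0 of 7 | about 1 of 7 |

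**2. What a between-arm effect requires**

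The mismatch in timing is the same in both arms. It cancels from the between-arm difference unless the arms respond to the request differently. Let Δ be the true gain in steps/day, f the share of that gain dropped on the pre-draw day, and D the number of valid days including that day. Then

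bias in an arm's mean change = −(Δ × f) / D.

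For controls, who are asked to carry on as usual, take Δ = 0. The bias in the between-arm difference is then the WMPD bias.

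**3. Inputs**

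- Δ = 3,000 steps/day, the WMPD target (section II.b). As an upper scenario, the pilot gain in section VII.b: 9,692 − 4,973 = 4,719.
- D = 7, the planned wear. As a low case, D = 4, the minimum in section VI, Baseline Visit, which is stated there for baseline compliance only.
- f is not in the documents. It is an assumption, ranged from 0 to 1. The formula also assumes that participants drop only added walking and none of their habitual activity.

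**4. Results (steps/day, with share of Δ)**

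| f | Δ = 3,000, D = 7 | Δ = 3,000, D = 4 |
|---|---|---|
| 0 | 0 | 0 |
| 0.25 | −107 (3.6%) | −188 (6.2%) |
| 0.5 | −214 (7.1%) | −375 (12.5%) |
| 1 | −429 (14.3%) | −750 (25%) |

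For example, 3,000 × 1 / 7 = 429 and 3,000 × 1 / 4 = 750. With the pilot gain and f = 1, the loss is 4,719 / 7 = 674 or 4,719 / 4 = 1,180. The percentages are unchanged.

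The documents give no MVPA values, so no figure in minutes is possible. Under the same assumptions the proportional bound also applies to a gain in MVPA: 0 to 1/7 with seven valid days, and up to 1/4 with four.

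**The case against.** The strongest reply is that the request is narrow. A reader might infer a compulsory day without exercise. The text asks participants to avoid a training session; it does not mention walking, the step goal or the pedal desk, and nothing tells WMPD participants to suspend their goals. The Innovation list in section II classes active-workstation use as something other than exercise, and people enrolled or planning to enrol in an exercise program are excluded (Table 2). Someone who reads the request literally and has no session planned changes nothing, so the bias is 0. Skipping the pedal desk would barely affect steps, because section II says that waist-worn counters largely miss pedaling.

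A reader might also infer that steps and MVPA are biased downward, mainly in WMPD. The documents do not establish that. The request applies to both arms, and a difference arises only if WMPD participants count their added walking as exercise.

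All of this stands and limits the claim to a possible attenuation. It does not remove the mismatch, and the protocol's vocabulary leaves room for the wider reading: section II.b calls MVPA exercise, and section VII describes pedal-desk use in sessions and speaks of adherence to exercise. WMPD participants are also the ones coached to add activity, so they have more to drop.

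The WMPD tracking data do show whether that arm's behaviour changed, but they provide no comparison with controls.

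**Conclusion.** The mismatch is in the text: the baseline week avoids the pre-draw period and the month-3 week contains it. Its consequence is possible but not established. Month-3 activity may be understated, most plausibly in WMPD, which would move the between-arm difference toward zero.

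At a gain of 3,000 steps/day, the attenuation is between 0 and 429 steps/day (14%) with full wear. The 750 (25%) figure needs both a complete stop of added walking for the day and only four valid days, one of them the pre-draw day. The range rests on an assumed share of activity dropped, for which the documents give no information.

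Only secondary accelerometer outcomes are involved. The primary visceral adipose tissue outcome and its sample size are unaffected. This is an inexpensive improvement and does not threaten the trial's main conclusion.

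**What to change.** **Main change.** In Month 3 Follow Up, have the accelerometer handed out at the workplace at least 8 to 9 days before the visit, and define the recorded window as seven days that close before the 24-hour pre-draw period. Eight days is enough only if the device is issued no later in the day than the draw: 8 − 7 = 1 day, exactly the 24 hours. Nine days leaves a margin of 9 − 7 = 2 days and also works if wear is counted in full calendar days from the day after issue. Because the device is still returned at the visit, the text should say that any wear after the seventh day is left out.

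**Where the hand-out cannot move.** Keep all valid days in the main summary and pre-specify a sensitivity analysis that excludes the pre-draw day in both arms. Exclusion should not be the main analysis. It takes a participant with four valid days to three, below the only wear minimum the protocol states. If the pre-draw day is a workday (visit days are not stated), it also changes the workday share of a full week from 5/7 (71%) to 4/6 (67%) at month 3 only.

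**Cost.** One sentence in the visit schedule and slightly earlier device logistics, with no added visit or procedure. The sensitivity analysis costs one recorded day per participant.
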